5. To evaluate patient management at ILD Center compared to outlying community centers among the groups and as stratified by class.
6. To evaluate a standardized protocol that includes a structured educational curriculum followed by a regularly timed disease-focused phone calls with protocolized interventions when disease progression is recognized.

Study Design

This is a single-center prospective randomized study to compare outcomes on hospitalization, healthcare compliance, and quality of life of telenursing with or without remote monitoring as compared to usual care. All patients diagnosed with IPF at the Vanderbilt Medical Center outpatient Pulmonary Clinic, who meet inclusion and exclusion criteria, will be asked to participate. Patients who agree to participate and sign consent will be randomized into one of three treatment arms: usual care (the control group), usual care with telenursing, usual care with telenursing and remote monitoring. Patients will be asked to participate in the study for at least one year. We expect to enroll 150 patients, or 50 patients into each arm.

Usual care (Arm 1) – Patients will continue to receive education in the clinic and telephonically about their lung disease, medications, and oxygen use. At the point of diagnosis, patients will be given our current educational materials to take home and review, as well as our contact information. Patients will continue to attend face-to-face visits in the out-patient setting. The frequency of visits will be based on the discretion of the provider. During these visits, the patient will continue to receive individualized standard of care, which may include some or all of the following: a face-to-face visit with a healthcare provider, vital signs, with pulse oximetry at rest, weight measurement, pulmonary function testing, a six-minute walk, and laboratory testing. Other testing, such as echocardiography or chest radiography, may be required based on need. If patients do not return to Vanderbilt Medical Center beyond the point of diagnosis, they will still be allowed to participate. The usual care of local healthcare providers will be collected.

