Data collected will include the following: demographics (gender, race, ethnicity, age at diagnosis, date of birth, miles from our center, classification of rural, suburban, or urban, tobacco use and status), diagnosis (date of diagnosis, where made, physician overseeing, where IPF healthcare will occur), longitudinal physiological components of IPF collected in the clinic or hospital (measures of pulmonary function, 6-minute walk, echocardiography, heartrate at rest, oxygen saturation at rest on room air/liter flow of oxygen, and body weight, as well as provider's interpretation of IPF classification/stage), daily physiological components as captured at home (FVC in liters, FEV1/FVC ratio, heartrate at rest, oxygen saturation at rest on room air/liter flow of oxygen), staging at clinic visits, use of FDA approved medications for IPF, hospitalizations (dates of admission and discharge to determine length of stay and time to hospitalization, and the admitting diagnosis), cost of hospitalizations, outcomes of telenursing calls, quality of life and other questionnaire scores, compliance measures (related to medications, pulmonary rehabilitation, oxygen use, and comorbidities such as GERD and OSA), and health status (living, deceased, transplanted). PHI collected will include date of birth, medical record number, date of diagnosis, and dates of service. No other standard PHI will be included.

Statistics

Power calculations for telenursing project

Simulation

In order to understand the operating characteristics of the proposed telenursing project, we constructed a simulation study. Using the Brown-2015 paper as the basis of the simulation study, we generated a hypothetical study cohort of 300 subjects (100 in each arm). The one-year hospitalization event rate was

set to 25% in the usual care arm (A1). The event rate in arm 2 (A2) and arm 3 (A3) was set to a range of values, as noted in results table below (“A2 risk” and “A3 risk”).

[figure not shown]

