We generated 4000 replicates of the hypothetical study cohort for each combination of event rates, i.e., the rows of the results table. In each replicate, we calculated the (a) overall treatment effect, (b) the A2 vs A1 effect, and (c) the A3 vs A1 effect. The effect estimates were calculated by fitting a logistic regression model, and corresponding tests were calculated with the Wald method. Power was calculated as the proportion of the 4000 replicates in which the treatment effect was significant at $\alpha=0.05$ type I error rate.

Results

The results are provided in the table below. In the plot, RR refers to the relative risk of arm 3 to arm 1. In the table and in the plot, relative risk (RR) is simply the ratio of the risk in arm 2 (or 3) divided by the risk in arm 1.

Code

```
plotstyle(style = upright); par(mar = c(3,3,2,1))
plot.new()
plot.window(xlim = sim_settings$N %>% range, ylim = c(0,1))
g <- sim_settings %>%
  as.data.table %>%
  `[,`(,lines(copy(N), copy(power), type = "b"),p2)
axis(1, at = sim_settings$N %>% unique)
axis(2)
box()
title(xlab = "N (per arm)", ylab = "Power")
g <- sim_settings %>%
  filter(N == max(N)) %>%
  as.data.table %>%
  `[,`(, text(N, power, "RR = " %|% round(rr2,2), adj= c(1,-1)))
```

The table and plot report the same information.

Sample Size	A1 risk	A2 risk	A3 risk	RR 2:1	RR 3:1	Power 3:2:1	Power 2:1	Power 3:1
50	0.25	0.23	0.22	0.93	0.86	0.07	0.05	0.06
100	0.25	0.23	0.22	0.93	0.86	0.08	0.06	0.08
150	0.25	0.23	0.22	0.93	0.86	0.09	0.06	0.10
200	0.25	0.23	0.22	0.93	0.86	0.11	0.07	0.13
250	0.25	0.23	0.22	0.93	0.86	0.12	0.07	0.15
300	0.25	0.23	0.22	0.93	0.86	0.14	0.08	0.17
50	0.25	0.22	0.19	0.87	0.75	0.10	0.05	0.10
100	0.25	0.22	0.19	0.87	0.75	0.14	0.08	0.17
150	0.25	0.22	0.19	0.87	0.75	0.21	0.10	0.26
200	0.25	0.22	0.19	0.87	0.75	0.25	0.11	0.32
250	0.25	0.22	0.19	0.87	0.75	0.31	0.14	0.39
300	0.25	0.22	0.19	0.87	0.75	0.36	0.15	0.45

Sample Size	A1 risk	A2 risk	A3 risk	RR 2:1	RR 3:1	Power 3:2:1	Power 2:1	Power 3:1
50	0.25	0.20	0.16	0.82	0.66	0.16	0.08	0.17
100	0.25	0.20	0.16	0.82	0.66	0.24	0.12	0.31
150	0.25	0.20	0.16	0.82	0.66	0.36	0.15	0.44
200	0.25	0.20	0.16	0.82	0.66	0.46	0.19	0.55
250	0.25	0.20	0.16	0.82	0.66	0.56	0.24	0.66
300	0.25	0.20	0.16	0.82	0.66	0.64	0.27	0.73
50	0.25	0.19	0.15	0.77	0.58	0.21	0.09	0.23
100	0.25	0.19	0.15	0.77	0.58	0.38	0.16	0.46
150	0.25	0.19	0.15	0.77	0.58	0.53	0.23	0.64
200	0.25	0.19	0.15	0.77	0.58	0.66	0.29	0.74
250	0.25	0.19	0.15	0.77	0.58	0.75	0.33	0.83

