300	0.25	0.19	0.15	0.77	0.58	0.84	0.38	0.90

At least 80% power for the joint treatment effect and the A3 vs A1 effect was achieved when the event rate was .25, .19, and .15 for the three arms, respectively. The power for the comparison between A2 and A1 was 0.38, which was the highest of all the situations considered.

Proposed statistical analysis plan for the primary endpoint

The primary endpoint will be an ordinal variable that is a composite of hospitalizations and death within one year of diagnosis. The categories of the ordinal variable will be: 0 hospitalizations & no death, 1 hospitalization & no death, ..., K hospitalizations & no death, and then death as the final category. This will order the patients from best to worst outcomes in a way that incorporates the possibility of death.

The primary endpoint will be analyzed with a cumulative probability ordinal regression model which includes treatment assignment indicators and relevant covariates, such as age, gender, race, and other measures of baseline disease severity like **time-since-diagnosis**. Continuous variables, such as age, will be included in the model with restricted cubic splines in order to allow for the possibility of a non-linear association with the outcome. Model diagnostics, such as DFBETAs, will be generated to identify overly influential observations.

Once the regression model diagnostics indicate the model is reasonably fit, the treatment effect will be tested with Wald statistics at the $\alpha=0.05$ type I error level. The first effect to be tested is the joint treatment effect. If the joint effect is significant, then A3 vs A1 and A2 vs A1 will be tested. If the joint effect is not significant, no additional pairwise comparisons will be tested. The sequential test strategy ensures that the type I error rate is preserved.

As a sensitivity analysis, we will analyze hospitalization rates (not the composite hospitalization and death) with a model similar to the one described above.

Every effort will be made to collect covariate information; however, if missing data exists in the analysis dataset, we will adjust the analysis described above and implement multiple imputation with predictive mean matching. At least 30 imputations will be generated.

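### The pairwise power columns give stand-alone powers, although the analysis plan tests each pair only after a significant joint test; A3 vs A1 power is overstated as a result

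*Combined protocol and SAP*

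**What the plan says.** All the relevant text is in the Statistics section of the combined protocol and SAP.

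- **Simulation.** In each replicate the joint treatment effect, A2 vs A1 and A3 vs A1 are each estimated from a logistic model and tested by the Wald method. "Power was calculated as the proportion of the 4000 replicates in which the treatment effect was significant" at the 0.05 level. Nothing says that a pairwise result counts only if the joint test succeeded.
- **Results.** The table gives Power 3:2:1 (joint), Power 2:1 and Power 3:1 for 50 to 300 patients per arm and four effect patterns. In the largest-effect pattern the 50-per-arm row reads "50 0.25 0.19 0.15 0.77 0.58 0.21 0.09 0.23" and the 300-per-arm row reads "300 0.25 0.19 0.15 0.77 0.58 0.84 0.38 0.90". The text then concludes: "At least 80% power for the joint treatment effect and the A3 vs A1 effect was achieved". It names the three event rates but not the sample size.
- **Proposed statistical analysis plan for the primary endpoint.** The joint effect is tested first. "If the joint effect is not significant, no additional pairwise comparisons will be tested".
- **Power for proposed analysis.** The tabled powers are presented as a lower bound for the planned ordinal analysis, because that analysis uses more of the outcome than a binary one.
- **Study Design.** "We expect to enroll 150 patients, or 50 patients into each arm".

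**The concern.** Under the plan's rule, a claim for A3 vs A1 needs two events: the joint test is significant, and the A3 vs A1 test is significant. The probability of both cannot exceed the probability of either one. A Power 3:1 figure larger than the Power 3:2:1 figure in the same row therefore cannot be the power of the stated procedure.

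At stake is whether the plan's figures describe the comparisons it will test. A reader takes Power 3:1 as the chance of showing that telenursing with remote monitoring differs from usual care. That chance is smaller than printed. At 250 per arm the printed figure is above 80% and the true figure for this procedure is below it.

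**Working it through.** **Inputs**

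- Sample size is per arm; the plotting code labels its axis that way. The planned size is 50 per arm (Study Design).
- Usual-care risk is 0.25 (Simulation).
- Largest-effect pattern: RR 0.77 and 0.58 (Results table). The risks are taken as 0.25 × 0.77 = 0.1925 and 0.25 × 0.58 = 0.145, because the rounded printed risks, 0.19 and 0.15, fit the table less well.
- The level is 0.05. Sidedness is not stated; two-sided is assumed.

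**Step 1: check from the printed table alone**

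Sequential power = P(joint significant and pair significant) ≤ min{P(joint), P(pair)}.

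Rows where Power 3:1 exceeds Power 3:2:1, from the smallest to the largest effect pattern: 4 + 5 + 6 + 6 = 21 of 24. In the largest-effect pattern the printed pairs (3:1 against joint) are 0.23/0.21, 0.46/0.38, 0.64/0.53, 0.74/0.66, 0.83/0.75 and 0.90/0.84. Simulation error does not explain these gaps. With 4000 replicates the standard error of 0.84 is √(0.84 × 0.16 / 4000) = 0.006, and the gap at 300 per arm is 0.06. In addition, all three effects were computed in each replicate, and within one set of replicates a sequential count can never exceed the joint count.

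At 250 per arm, sequential A3 vs A1 power is therefore at most 0.75, whatever the correlation between the tests.

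**Step 2: reproduce the printed pairwise columns**

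Method: three binomial arms, unadjusted logistic model, two-sided Wald tests, 400,000 replicates per row. With each pair tested on its own, power at 50 per arm is 0.238 for A3 vs A1 (printed 0.23) and 0.095 for A2 vs A1 (printed 0.09). Both pairwise columns are matched within 2 points in all 24 rows. The columns are stand-alone powers.

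**Step 3: apply the plan's rule**

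The same replicates are used, but a pairwise success counts only if the 2-df joint test is also significant. The text specifies a Wald joint test, but at 50 per arm that gives a joint power of 0.171 against the printed 0.21. A likelihood-ratio joint test gives 0.214. Both are shown.

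Largest-effect pattern, A3 vs A1:

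| Per arm | Printed | Stand-alone, recomputed | Sequential, Wald joint | Sequential, LR joint |
|---|---|---|---|---|
| 50 | 0.23 | 0.238 | 0.146 | 0.177 |
| 100 | 0.46 | 0.457 | 0.329 | 0.347 |
| 150 | 0.64 | 0.629 | 0.496 | 0.509 |
| 200 | 0.74 | 0.754 | 0.636 | 0.646 |
| 250 | 0.83 | 0.843 | 0.747 | 0.753 |
| 300 | 0.90 | 0.901 | 0.828 | 0.832 |

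At 50 per arm the relative loss, like for like, is (0.238 − 0.177)/0.238 = 26% with the LR joint test and (0.238 − 0.146)/0.238 = 39% with the Wald joint test.

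Same pattern, A2 vs A1:

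| Per arm | Printed | Stand-alone, recomputed | Sequential (Wald to LR joint) |
|---|---|---|---|
| 50 | 0.09 | 0.095 | 0.072–0.076 |
| 100 | 0.16 | 0.161 | 0.138 |
| 150 | 0.23 | 0.222 | 0.201–0.202 |
| 200 | 0.29 | 0.279 | 0.265 |
| 250 | 0.33 | 0.340 | 0.330 |
| 300 | 0.38 | 0.395 | 0.388–0.389 |

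**Step 4: sensitivity**

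With the rounded risks 0.19 and 0.15 at 50 per arm, sequential A3 vs A1 power is 0.134 (Wald joint) to 0.161 (LR joint). In the RR 0.82/0.66 pattern at 50 per arm, the printed 0.17 becomes 0.096 to 0.116.

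**The case against.** The best defence is that the printed figures are correct for what the Simulation text describes: three effects per replicate, each with its own test. They reproduce, so this is not an arithmetic slip. The joint power stands beside the pairwise powers in every row, and the testing rule is stated openly, so a careful reader can see that 0.23 is capped at 0.21. All of that stands. It does not cure the mismatch, because no text tells the reader to apply the cap, and the sentence about 80% power names A3 vs A1 without mentioning the rule.

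The defence can also say that the planned analysis is an ordinal, covariate-adjusted model and may be more powerful. That may be so, but the plan gives no power figure for it. The lower-bound argument compares an ordinal outcome with a binary one and leaves out the joint-test requirement, which pushes pairwise power down.

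Four stronger readings are tempting, and the documents do not support them:

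- *None of the stated pairwise powers can be reached.* This fails for A2 vs A1 in the largest-effect pattern at 250 to 300 per arm, where the printed 0.33 and 0.38 compare with sequential 0.33 and 0.39.
- *The 80% sentence is false.* Its joint-power part is met only in the 300-per-arm row, and there sequential A3 vs A1 power is still about 0.83.
- *The trial's actual A3 vs A1 power is 0.15.* That figure rests on a Wald joint test that does not reproduce the printed joint power at 50 per arm, and on an unadjusted binary outcome.
- *The plan withholds pairwise estimates when the joint test fails.* The rule restricts testing. It does not forbid reporting odds ratios with intervals, and whether to promise them is a separate choice.

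**Conclusion.** The point holds as a mismatch between the power table and the test procedure, and it falls mainly on A3 vs A1. That 21 printed A3 vs A1 figures exceed their own ceiling follows from the documents alone. The size of the overstatement comes from simulation of the unadjusted binary analysis, with risks of 0.25 × tabled RR and two-sided 0.05. In the largest-effect pattern the printed A3 vs A1 power is too high by about 5 to 8 points at 50 per arm, 11 to 13 at 100, 8 at 250 and 7 at 300.

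No design decision turns on it. At the planned 50 per arm, A3 vs A1 power is far below 80% with or without the joint-test requirement, and the testing rule itself is not in question. This is a correction to stated operating characteristics that is worth making, not a fault that invalidates the trial.

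**What to change.** 1. Re-run the simulation, counting a pairwise success only when the joint test is also significant. Use the same joint test as the analysis plan (Wald, as written), and settle why the printed joint powers at small sizes match a likelihood-ratio test better.
2. Replace the Power 2:1 and Power 3:1 columns with these figures, or add the new figures and label the existing columns as stand-alone powers that ignore the joint test.
3. In the 80% sentence, state that it applies at 300 per arm and that A3 vs A1 power under the sequential rule is about 0.83 there.
4. Under Power for proposed analysis, stop calling the stand-alone pairwise columns a lower bound. Either limit that statement to the outcome scale or support it with a simulation of the ordinal model under the sequential rule.

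The cost is one added condition in the simulation code and a few revised figures and sentences. The stated pairwise powers become less favourable. Sample size and the test rule do not change.

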Power for proposed analysis. The proposed analysis is expected to be more powerful than the analysis simulated above because it uses an ordinal instead of a binary outcome. As such, the power calculations above serve as a lower bound for the analysis of the primary endpoint.

APPENDICES

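### The 80% power statement belongs to 300 patients per arm; at the planned 50 per arm the plan's own table gives 21% for the joint test

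*Combined protocol and SAP*

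**What the plan says.** Four places in the combined protocol and SAP bear on this.

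- **Study Design:** "We expect to enroll 150 patients, or 50 patients into each arm".
- **Statistics, Simulation:** "we generated a hypothetical study cohort of 300 subjects (100 in each arm"). The usual-care one-year hospitalization rate is set at 25%. The tests are described as follows: "The effect estimates were calculated by fitting a logistic regression model, and corresponding tests were calculated with the Wald method".
- **Statistics, Results:** the table covers 50 to 300 patients under four sets of event rates, and the plot code labels that axis as per arm. The text below the table says "At least 80% power for the joint treatment effect and the A3 vs A1 effect was achieved when the event rate was" 0.25, 0.19 and 0.15. It continues: "The power for the comparison between A2 and A1 was 0.38", described as the best value in the grid. Neither sentence gives a sample size.
- **Primary endpoint analysis and its power paragraph:** the joint test acts as a gate: "If the joint effect is not significant, no additional pairwise comparisons will be tested". The planned outcome is ordinal, and the plan says that "the power calculations above serve as a lower bound for the analysis of the primary endpoint".

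**The concern.** The only conclusion drawn from the power table is tied to event rates and to no sample size, so it reads as the power of the trial being proposed. The Simulation section adds to the risk. It describes a cohort of 300 in total, so a reader who meets the 300 row may take it for a whole trial of 100 per arm. Three sizes are therefore in play (50, 100 and 300 per arm), and the results text never gives the power at the size to be enrolled.

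The gate raises the stakes. If the joint test fails, neither intervention arm is formally compared with usual care. A trial believed to have 80% power that returns a null result will be read as evidence against telenursing. If its power is nearer 20%, a null result is the expected outcome even when the larger assumed effect is real.

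**Working it through.** **Inputs.** Planned size: 50 per arm (Study Design). Tests: two-sided 0.05, Wald, with 2 degrees of freedom for the joint test. Risks: the table prints rounded values, so I used 0.25 times the printed relative risks.

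- Arm 2: 0.25 × 0.77 = 0.1925
- Arm 3: 0.25 × 0.58 = 0.145

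**Step 1: find the row behind the sentence.** At these rates the table prints:

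| Per arm | Joint | Arm 2 vs 1 | Arm 3 vs 1 |
|---|---|---|---|
| 50 | 0.21 | 0.09 | 0.23 |
| 250 | 0.75 | 0.33 | 0.83 |
| 300 | 0.84 | 0.38 | 0.90 |

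Only the 300 row has both joint and Arm 3 vs Arm 1 power at 0.80 or above. In the Arm 2 vs Arm 1 column, 0.38 appears only there. The total is 3 × 300 = 900 patients, and 900 / 150 = 6 times the plan.

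**Step 2: reproduce the pairwise figures by hand.** Power ≈ Φ(|log OR| / SE − 1.96), where SE² is the sum of the reciprocals of the expected events and non-events in the two arms.

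Arm 3 vs Arm 1:
- OR = (0.145/0.855) / (0.25/0.75) = 0.509, so |log OR| = 0.676.
- 50 per arm: SE = √(1/12.5 + 1/37.5 + 1/7.25 + 1/42.75) = 0.518. Power = Φ(1.305 − 1.96) = 0.26.
- 300 per arm: SE = 0.518/√6 = 0.211. Power = Φ(3.197 − 1.96) = 0.89.

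Arm 2 vs Arm 1:
- OR = (0.1925/0.8075) / (0.25/0.75) = 0.715, so |log OR| = 0.335.
- 50 per arm: SE = √(1/12.5 + 1/37.5 + 1/9.625 + 1/40.375) = 0.485. Power = Φ(0.691 − 1.96) = 0.10.
- 300 per arm: SE = 0.198. Power = Φ(1.693 − 1.96) = 0.39.

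**Step 3: rerun the simulation.** Three arms, unadjusted logistic model, Wald tests, 400,000 replicates; replicates with a zero-event arm counted as non-significant.

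| Per arm | Joint | Arm 2 vs 1 | Arm 3 vs 1 | Arm 2 vs 1 after gate | Arm 3 vs 1 after gate |
|---|---|---|---|---|---|
| 300 | 0.835 | 0.393 | 0.901 | – | 0.828 |
| 50 | 0.171 | 0.095 | 0.239 | 0.071 | 0.146 |

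The 300 row reproduces to within two percentage points. Reading N as a total fails: 100 per arm gives about 0.36 / 0.16 / 0.46. The column is therefore per arm. Between the tabulated sizes, the joint Wald test reaches 0.80 at about 275 per arm (825 patients).

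The printed joint power of 0.21 at 50 per arm does not reproduce with the stated Wald test (0.17). A likelihood-ratio test gives 0.213 and Pearson's test 0.198. The test code is not shown, so the method used for that column cannot be established. With the printed rates 0.25/0.19/0.15 taken literally, the Wald joint power at 50 per arm is 0.160.

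**Step 4: test the lower-bound claim.** The plan gives no category rates, so those below are assumptions. Proportional-odds model, Wald joint test, no covariates, 50 per arm, 5,000 replicates.

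Treatment shifts the whole scale, deaths included (odds ratios 0.715 and 0.509):

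| Control: 0 / 1 / 2+ hospitalizations / death | Joint power |
|---|---|
| 75 / 13 / 4 / 8% | 0.167 |
| 75 / 10 / 5 / 10% | 0.164 |
| 65 / 17 / 6 / 12% | 0.236 |
| 55 / 22 / 8 / 15% | 0.296 |

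Treatment changes hospitalization among survivors only (0.25/0.1925/0.145), with deaths equal across arms at 5, 10 or 15%: joint power 0.121, 0.112 and 0.099.

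**Step 5: what one result would look like.** At 50 per arm the expected Arm 3 vs Arm 1 odds ratio of 0.51 carries a 95% interval of exp(−0.676 ± 1.96 × 0.518), about 0.18 to 1.40.

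**The case against.** The strongest reply is that nothing is hidden. The 50-per-arm rows are printed for all four scenarios just above the sentence. The sentence only reports where in the grid 80% was reached, and the next one signals a best case. The plan nowhere says that 50 per arm was chosen to reach 80%, and no figure in the sentence is miscalculated. This stands as a description: the fault is an omitted sample size and an unacknowledged low power, not a false number. It does not rescue the text, because the only stated conclusion comes from a row six times the planned size.

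Three narrower points also stand.

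- 300 per arm is the threshold only among the sizes tabulated. The joint test crosses 0.80 near 275, and Arm 3 vs Arm 1 alone is already 0.83 at 250.
- Whether joint power is 0.17 or 0.21 at 50 per arm changes no conclusion, so the Wald discrepancy is a side note.
- The ordinal figures rest on assumed rates and omit the planned covariate adjustment, so they are not the power of the exact planned model. Where treatment shifts deaths too, they are mostly at or above the binary figure, so the plan's expectation may prove right. In the equal-death cases a like-for-like binary comparison (hospitalized and alive) is itself only about 0.16, 0.15 and 0.13. The ordinal values are still lower, by less than a comparison with 0.17 suggests. The lower bound is unproven rather than generally wrong.

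**Conclusion.** The concern holds, and the statement is wrong as written for this trial. The 80% and 0.38 figures describe 900 patients. At the planned 150, under the most favourable rates considered, the plan's table gives 0.21 / 0.09 / 0.23 (joint / Arm 2 vs 1 / Arm 3 vs 1). The stated tests give about 0.17 joint and, after the gate, 0.07 and 0.15 for the two comparisons.

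The core finding needs no assumption beyond reading the table with its per-arm label, which the reruns confirm. The reruns assume risks inferred from the printed relative risks and no dropout, since the power section states none. The ordinal range of about 0.10 to 0.30 depends on assumed category rates and on leaving out covariates, but every case examined is far below 80%. Correction is essential, because the sentence is the plan's only summary of its power.

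**What to change.** Needed to correct the text:

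1. In the Results text, attach 300 per arm (900 patients) to the 80% sentence and to the 0.38, and state the power at 50 per arm beside them, labelled as power for the binary endpoint.
2. In the Simulation section, say that sizes from 50 to 300 per arm were simulated, in place of the single cohort of 100 per arm.
3. Rerun the 50-per-arm rows with the stated Wald tests, or name the test actually used for the joint column.
4. Replace the lower-bound sentence with power for the planned ordinal model at 50 per arm, on stated category rates, including a case with equal deaths in all arms.

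Advisable as well:

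5. Report pairwise power after the joint-test gate.
6. State that a non-significant result at this size will be reported with confidence intervals and not read as absence of effect.

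The cost is protocol and SAP wording, a rerun of the existing simulation and one added ordinal simulation. No extra patients are needed. The stated power becomes much less favourable.
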